## Purpose and Justification

A key driver of inappropriate care is patient expectations; that is, patients want something done when they seek care, whether that be a diagnostic test or some form of intervention such as a prescription[1, 2]. There is a growing body of literature providing evidence that increasing knowledge and awareness among patients can influence their behaviours in terms of deciding to seek care or expectations of healthcare professionals if they do seek care[3, 4]. Moreover, behaviour theory indicates that precursors to behaviour change are awareness, knowledge, and intentions.[5-7] Knowledge translation (KT) is concerned with the communication of evidence to improve such outcomes.

In the context of pediatric healthcare, connecting parents and legal guardians to research evidence has the power to improve health decision-making and reduce health system costs[8]. The heaviest users of unscheduled healthcare are children, who also make up a large proportion of emergency department (ED) attendances that may have been treatable elsewhere (e.g. primary care or home)[9]. There are multiple complex factors and circumstances that can influence parents' decision-making regarding where, when and why they seek unscheduled healthcare for their children. A recent systematic review highlighted that pressure to be seen as 'doing the right thing' as a parent was related to care seeking[10]. However, fear of wasting a doctor's time for a minor illness was perceived as a barrier for seeking care[10]. Subsequently, parents and caregivers should be the target of efforts to promote empowerment. Parent empowerment can be defined as the "process through which parents are able to increase the control they have over decisions and actions affecting their child's health[11]". One mechanism for supporting and empowering parents could be through KT of the Choosing Wisely Canada (CWC) recommendations.

It has become increasingly clear that parents need knowledge and confidence to be involved in healthcare decisions. CWC is a national movement launched in 2014 in partnership with the Canadian Medical Association. The campaign aims to help physicians, patients and families engage in conversations around unnecessary tests, treatments and procedures, which often do more harm than good and result in significant waste in the Canadian healthcare system. The central tenant to the movement is specialty-specific lists of "Things Physicians and Patients Should Question" aimed to assist physicians and patients in making informed health choices. Further, parents often seek care for these conditions either from their primary care provider or through the ED, representing a large burden on healthcare resources[13-17]. While there are a number of pediatric specific CWC recommendations[18, 19], there is currently no outward facing CWC campaign that targets parents in the community.

In the pediatric context, conditions such as ear infections, the common cold, sore throat, bronchiolitis and asthma are extremely common among children in Canada. These are conditions in which antibiotic treatment is usually unnecessary, however antibiotics are often prescribed[12]. Our goal is to co-design with parents an intervention and evaluation of CWC recommendations that align with common childhood conditions. We have previously evaluated different means of sharing health information with parents and found that blogshots compared to plain language summaries and Wikipedia pages showed significant differences in terms of parent preferences, knowledge and usability[13]. This study will include all four elements of the CWC patient

UofA Ethics ID: Pro00116449.

NCT ID not yet assigned

July 19, 2023

engagement framework[14]. We will **partner** and **engage** with parent stakeholders to design and create blogshots that are tailored to parents. We will then assess the effectiveness of the blogshots at **informing** and educating parents on CWC recommendations and **empowering** them to make educated, evidence-based choices for their child's health. To our knowledge, this study will be the first of its kind in Canada, and has the potential for widespread scale and implementation.

## Objective

Our objective is to assess the effectiveness of blogshots to increase parent awareness, knowledge and expectations with respect to CWC recommendations that align with common childhood conditions.

## Research Methods/Procedures

This is a multi-method study including a randomized control trial (RCT) and qualitative interviews. While the RCT will provide quantitative estimates of effectiveness, the qualitative component will help us understand how the intervention works. Ethics approval will be sought through the University of Alberta Human Research Ethics Board (HREB). The trial will be registered on the ClinicalTrials.gov database after ethics approval.

### Inclusion Criteria

- Over the age of 18 years
- Parent or legal guardian of a child under 5 years of age
- Live in Canada
- Able to complete the questionnaire and interview in English (speak/read)
- Access to an electronic device (e.g. computer, tablet or smart phone), Internet and email.

### Exclusion Criteria

- Under the age of 18 years
- Does not identify as a parent or legal guardian of a child under 5 years of age
- Does not live in Canada
- Unable to complete the interview and questionnaire in English (speak/read)
- No access to an electronic device (e.g. computer, tablet or smart phone), Internet and email.

**Recruitment:** Recruitment will begin once the study has received ethics approval. We will engage with our Pediatric Parent Advisory Group (P-PAG) to co-develop a recruitment strategy with our target stakeholders [15]. Parents will be recruited from across Canada using an online approach. Recruitment will take place primarily via social media and other networks such as the P-PAG and the Pediatric Parent Consultation Network (P-PCN) with which we have established connections. The ARCHE and ECHO research teams are well positioned to perform social media recruitment as we have an established social media presence on Twitter: @arche4evidence, @echoKTresearch, @ArcheEchoKT, Instagram: arche4evidence, ArcheEchoKT, Echoktoofficial, Facebook: Echo Research and Reddit: u/ArcheEchoKT.

We have developed a list of stakeholder networks with social media handles and will perform an extensive social media recruitment campaign. A recruitment email will be sent to stakeholder groups in Canada to inform about the study and ask to share the study materials with their contacts.

**Consent Process:** Implied consent by overt action will be sought for the questionnaire portion of the study. Participants will confirm consent by continuing on and completing the questionnaire. Participants will be able to access and read the informed consent document and have the option to download the consent form from the questionnaire platform hosted by Nooro. For the qualitative interview portion, verbal consent will be obtained on Zoom video conferencing software prior to starting the interview and documented in the study verbal consent log.

### Study Design: RCT

Participants will be randomized to two groups: Group A or Group B; each will receive messages over 4 weeks that will consist of blogshots for different CWC recommendations [18]. Participants who complete the baseline questionnaire will receive one blogshot via email every week for three weeks and the fourth week will include a summary of all three blogshots. This will be automated through the Nooro platform. Through the Nooro platform we will monitor if participants have opened the email and viewed the blogshot. If an email has not been opened for 3 days, a reminder email will be sent. At the end of the four-week campaign, participants will be asked to complete a follow-up questionnaire after the intervention at week 5 and then at three and six months post-intervention. The group topics will be:

Group A;

- *Don't routinely do a throat swab when children present with a sore throat if they have a cough, rhinitis, or hoarseness;*
- *Don't recommend the use of cough and cold remedies in children under six years of age;*
- *Don't use antibiotics for acute asthma exacerbations without clear signs of bacterial infection.*

[figure not shown]
Group B;

- *Don't routinely use antibiotics in children with uncomplicated sore throats;*
- *Don't prescribe antibiotics in adults with bronchitis/asthma and children with bronchiolitis;*
- *Don't use antibiotics in adults and children with uncomplicated acute otitis media.*

**Randomization:** Blocked randomization with randomly chosen block sizes will be used to ensure equal distribution of participants to each study arm. The blocked randomization sequence will be computer generated. Parents will be randomized to either group A or group B when completing the demographic and baseline questionnaire on the electronic platform.

**Sample Size:** We will aim to recruit 180 parents (90 participants per group). This is based on assuming a 10% difference between groups in knowledge scores and a standard deviation of 2.0

with 80% power. This would require 64 participants per group and we have increased this number by 25% to allow for dropouts.

**Figure 1: Study Design**

**Blogshot Development:** Six blogshots were developed with the assistance of a graphic designer. Members of the P-PAG provided feedback on the language, design and content of the blogshots.

**Online Questionnaire Development:** The research team developed four questionnaires (baseline and 3 follow-up questionnaires). The questionnaires consist of multiple choice knowledge questions based on the information presented in the blogshots, questions about participant’s intentions for managing common acute childhood conditions and actions participants took if their child developed symptoms of one of the conditions from the blogshot during the duration of the study. A series of 7 questions about the usability of the blogshots will be included in the questionnaire as well.

The questionnaire is designed and housed in the Nooro platform (<https://nooro.com>). An overview of each question category is listed below:

**Baseline Questions:** Four baseline questions will be included about parent’s experience with the common acute childhood conditions included in the blogshots as well as number of times they went to the emergency department or received a prescription for antibiotics for their child. A question about information seeking is also included. **These questions are asked at baseline.**

**Knowledge Questions:** Each topic will have three “core” knowledge questions that will be included at baseline and all three follow-up questionnaires. An additional knowledge question will be included for each topic in which a participant received a blogshot. For example, group A will

receive one extra question for the sore throat swab, cough and cold medication and bronchiolitis topic and group B will receive an extra question on acute otitis media, asthma exacerbations and sore throat. **These questions are asked at baseline, follow-up 1, follow-up 2 and follow-up 3.**

**Expectation Questions:** Each blogshot topic will have 1 expectation question that asks parents about their expectations from a healthcare provider on the management and treatment of each condition. **These questions are asked at baseline and follow-up 1.**

**Intention Questions:** Each blogshot topic will have one intention question that asks parents about their intentions on the management and treatment of each condition. **These questions are asked at baseline and follow-up 1.**

**Actions Questions:** Participants will be asked about actions they took during the course of the study in follow-up 2 and 3. For example if their child had symptoms related to information in the blogshot and the actions they took i.e. went to a physician, filled a prescription for antibiotics, etc.

**Usability Questions:** Usability questions about the blogshot will be included at follow-up 1. These are usability questions previously developed by ARCHE ECHO.

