## Outcomes

The will be knowledge immediately after the campaign; we will compare change from baseline between groups (i.e. average change in knowledge scores specific to CWC recommendations, expecting that knowledge will improve with respect to the content received). Secondary outcomes will be intentions, expectations of care and usability of the blogshots. We will explore if outcomes were influenced by whether a child had one of the conditions (and identify actual behaviour). All outcomes will be assessed both quantitatively through questionnaire responses and qualitatively through the semi-structured interviews.

The outcomes will focus on the following 5 domains:

**Knowledge:** Knowledge will be assessed by comparing participant's scores on baseline questionnaire to follow-up questionnaire 1 (knowledge change) and comparing scores to follow-up questionnaires 2 and 3 (knowledge retention).

**Expectations:** Participants will be asked questions about their expectations of healthcare professionals at baseline and follow-up 1 questionnaires. We will compare at baseline and follow up to assess if the blogshots led to a change in expectations of healthcare professionals.

**Intentions:** Participants will be asked questions about their intentions at baseline and follow-up 1 when they seek healthcare i.e. are they seeking antibiotics from a healthcare professional.

**Actions:** Participants will be asked about actions they took during the course of the study in follow-up questionnaires 2 and 3. For example if their child had symptoms related to information in the blogshot and the actions they took i.e. went to a physician, filled a prescription for antibiotics, etc.

**Usability of the blogshots:** Participants will complete usability questions about the blogshots focusing on topics such as if the blogshots increase knowledge, aid in decision-making and are relevant to parents. This will be completed at follow-up 1.

The semi-structured interviews will include questions on all 5 of these domains to clarify, expand on and provide to context to the questionnaire responses.

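### Advisory-group parents who reviewed the blogshots are not barred from the trial, which could slightly dilute the knowledge contrast and make some usability ratings non-independent

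*Combined protocol and SAP*

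**What the plan says.** All statements are in the combined protocol and SAP.

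- **Development.** Six blogshots were made, which is the number needed for both arms at three topics each. The Blogshot Development paragraph adds: "Members of the P-PAG provided feedback on the language, design and content of the blogshots". It does not limit the feedback to one arm's material. It also does not say that every member saw every blogshot.
- **Recruitment.** The Recruitment paragraph, under Exclusion Criteria, reads: "Recruitment will take place primarily via social media and other networks such as the P-PAG". The parent consultation network (P-PCN) is named alongside it.
- **Eligibility.** The relevant inclusion criterion is "Parent or legal guardian of a child under 5 years of age", and its counterpart among the exclusions is "Does not identify as a parent or legal guardian of a child under 5 years of age". The other criteria cover age, residence in Canada, English, and device, Internet and email access. None concerns part in development or earlier sight of the blogshots.
- **Outcome.** The questionnaires contain "multiple choice knowledge questions based on the information presented in the blogshots". For the main knowledge outcome, the Outcomes section says "we will compare change from baseline between groups". Usability is a secondary outcome.
- **Analysis.** Plan for Data Analysis has no sensitivity analysis for prior exposure.

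**The concern.** Each arm is the comparison for the other arm's topics, so the contrast depends on participants learning the tested content from the blogshots they are allocated. A parent who commented on the content during development has already met some of the tested material, possibly including the other arm's. Such a parent may score higher at baseline and have less room to improve, and so add less to the arm difference.

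The usability outcome is touched more directly. It is a rating of the blogshots received, so randomisation does not correct for a rater who helped shape them. The same holds for the interviews, where participants volunteer and the target is about 30. Three reviewers among them would be 3/30 = 10% of that sample.

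The described baseline questionnaire has no item on earlier involvement. Names and email addresses are held during data collection and could in principle be matched to a membership list. The plan does not provide for this, and the identifiers are removed from the data files once collection ends.

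**Working it through.** **Step 1. Can a reviewer be randomised under the plan as written?** Reviewing the blogshots is not an exclusion. The P-PAG is a named recruitment network. A reviewer with a child under 5 who meets the other criteria therefore qualifies. The text permits enrolment but does not say that it is planned.

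**Step 2. Reproduce the plan's sample size.** The Sample Size paragraph gives its basis as "assuming a 10% difference between groups in knowledge scores and a standard deviation of 2.0", with 80% power and 64 per group. The significance level is 0.05, taken as two-sided from the two-sided 95% confidence intervals in Plan for Data Analysis. The score range is not stated, so the absolute difference is not given. A difference of 1.0 point (10% of a 10-point scale) is an assumption, adopted because it returns the stated figure:

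- Standardised difference d = 1.0/2.0 = 0.5.
- Normal approximation: n = 2 × (1.960 + 0.842)² / 0.5² = 62.8, so 63 per group.
- Two-sample t-test: n = 63.8, so 64 per group. This matches the plan.

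**Step 3. Model for dilution.** Let f be the share of analysed participants who were pre-exposed. As a worst case, suppose they show no arm difference at all and the SD is unchanged. The mean effect becomes 1.0 × (1 − f), so d = 0.5 × (1 − f). The documents give neither the size of the P-PAG nor the number of eligible reviewers, so every value of f is an assumption.

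**Step 4. Sample size left for analysis.** The plan recruits 90 per group and speaks of a 25% allowance for dropout. If 25% drop out, 90 × 0.75 = 67.5, so 67 to 68 per group remain.

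**Step 5. Power (two-sided t-test, alpha 0.05).**

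| f | d | 64 per group | 67 per group | 68 per group |
|---|---|---|---|---|
| 0 | 0.500 | 80.1% | 81.9% | 82.5% |
| 3% | 0.485 | 77.7% | 79.6% | 80.2% |
| 5% | 0.475 | 76.0% | 77.9% | 78.5% |

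In people, at 64 per group (128 analysed), 3% is 128 × 0.03 ≈ 4 and 5% is 128 × 0.05 ≈ 6.

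**Step 6. Direction.** Reviewers would be allocated at random like everyone else, so they are expected equally in both arms. Knowledge is also measured at baseline and analysed as change. The expected effect is a shift towards zero, not towards either arm.

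**The case against.** The strongest reply is that recruiting through a group is not the same as enrolling its members. The Recruitment paragraph says the P-PAG will help develop the recruitment strategy, and that stakeholder groups will be asked to pass the study materials to their contacts. On that reading the P-PAG is a channel for the advert. This reading is reasonable and may be the intention, but the text does not say so, and members who respond to the advert are not barred.

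The second reply is that the numbers must be small. A reviewer needs a child under 5, must choose to enrol and must complete follow-up. This stands, and it limits how serious the point is.

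The third reply is that the plan has a margin: 90 per group are to be recruited against 64 required. This also stands. With 25% dropout and 3% pre-exposed, power stays at about 80%. The margin does not make usability ratings or interviews independent.

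A reader might infer more than the documents support:

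- *Pre-exposed parents would start near the maximum score on both topic sets.* No baseline scores, item difficulty or interval between review and baseline are given, and the text does not say that any one member reviewed all six blogshots. The assumption of no arm difference in the working is therefore a worst case.
- *Power could fall to about 71%.* This needs 10% pre-exposed (about 13 of 128 analysed) and exactly 64 per group. The first has no source in the documents, and the second ignores the recruitment margin.

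**Conclusion.** The gap is real but modest. The plan as written can randomise parents who have already seen some of the tested material and helped shape the product they would rate. The documents do not show that any such parent would enrol.

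For the knowledge contrast, the expected consequence is slight dilution. In the worst-case model this costs about 2 percentage points of power at 3% pre-exposed and 4 at 5%, much of which the recruitment margin offsets. These figures rest on an inferred 1.0-point difference, an assumed pre-exposed share, and no arm difference among those parents. A reader might also infer that the trial is biased in favour of one arm or exposed to a false positive result. Random allocation and the comparison of change from baseline give no support for either.

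For usability and the interviews, the issue is independence of the raters. It is not measured by power and does not shrink with a larger sample. The case for acting rests on how little the remedy costs, not on a threat to the main result.

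**What to change.** Add one exclusion criterion: *took part in developing or reviewing the study blogshots or questionnaires*. Add a matching yes/no screening item, answered before randomisation. State in the Recruitment paragraph that the P-PAG may still share the advert with its contacts.

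The cost is one criterion, one screening question and at most a handful of potential participants. The required 64 per group does not change.

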## Data Collection

The following data will be collected over the course of the study:

1. **Baseline questionnaire:** Participants will complete a pre-intervention questionnaire that includes demographics, knowledge about antibiotic use and common acute childhood conditions, intentions about whether they would seek healthcare for their child for a

common childhood condition and their expectations on management by healthcare providers.

2. **Follow-up questionnaire 1 (5 weeks after baseline):** Participants will re-do all knowledge, intentions and expectation questions as well as provide feedback on the blogshot design.
3. **Follow-up questionnaire 2 (3 months after baseline):** Participants will re-do knowledge questions (knowledge retention). They will also be asked action questions about whether their child experienced any of the conditions and what actions they took (e.g. sought healthcare services, over the counter medications, filled prescriptions).
4. **Follow-up questionnaire 3 (6 months after baseline):** Participants will re-do knowledge questions and action questions.
5. **Qualitative Interviews (post intervention):** Interviews will be conducted over zoom video conferencing software and recorded and transcribed using a third-party transcriptionist.

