## Plan for Data Analysis

**Questionnaire Data:** Demographic data will be collected to evaluate how representative our sample is to the Canadian population. We will use descriptive statistics, including numbers, frequencies, and means, to present demographic data. Group differences will be evaluated using independent t-test or chi squared and baseline and follow-up will be evaluated using paired t-tests or Wilcoxon signed rank test, dependent on distribution of data. In all analyses, statistical uncertainties will be expressed in 95% two-sided confidence intervals. A p value of <0.05 will indicate statistical significance. Analyses will be conducted based on intention-to-treat[20].

**Interview Data:** The project coordinator will perform an inductive thematic analysis of the interview data[21]. Interview coding and analysis will occur concurrently with data collection using an iterative approach. In this approach, data will be categorized into codes, forming categories that are then combined into themes that can be thoroughly described in the results. Lincoln and Guba's criteria will be used to establish trustworthiness of the analytic process[22]. Qualitative data analysis software NVIVO will be used to organize and code the data[23].

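### Baseline counts of ED visits and antibiotic prescriptions are collected but given no role, so the exploratory comparison of actions is left unadjusted for prior use

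*Combined protocol and SAP*

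**What the plan says.** Under Online Questionnaire Development, the Baseline Questions cover parents' "experience with the common acute childhood conditions included in the blogshots" together with the "number of times they went to the emergency department or received a prescription for antibiotics for their child". They are marked as asked at baseline. No look-back period is stated.

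Actions are collected later: "Participants will be asked about actions they took during the course of the study in follow-up 2 and 3". The Actions Questions paragraph gives as an example "the actions they took i.e. went to a physician, filled a prescription for antibiotics, etc", and the Actions entry under Outcomes repeats it. Data Collection, item 3, is broader: parents say whether their child had any of the conditions and "what actions they took (e.g. sought healthcare services, over the counter medications, filled prescriptions".

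Outcomes lists actions as one of five domains. Its secondary outcomes are intentions, expectations and usability; actual behaviour appears only in the sentence on what will be explored.

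The Plan for Data Analysis says: "Group differences will be evaluated using independent t-test or chi squared". It adds paired tests of baseline against follow-up without naming variables. It names no covariate, no model for actions and no use of the baseline counts.

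**The concern.** Actions is the only one of the five domains that records what parents did rather than what they know, expect, intend or think of the blogshots. Prior ED and antibiotic use is a plausible predictor of later use, and the trial already asks for it. An unadjusted test ignores it. If one arm happens to contain more families with heavy prior use, that imbalance stays in the estimate and widens its uncertainty.

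The sample was sized for the knowledge score, so an actions comparison has no precision to spare. ED attendance is also part of the trial's rationale, which describes children as those "who also make up a large proportion of emergency department (ED) attendances that may have been treatable elsewhere". It is therefore natural to ask whether prior and later use are recorded in terms that can be linked.

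**Working it through.** The plan gives no figure on this point to reproduce. The check is a comparison of sections, followed by an illustration under an assumed correlation.

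**1. How use is described at each time**

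- Baseline (Baseline Questions): number of ED visits; number of antibiotic prescriptions received; no look-back stated.
- Follow-ups 2 and 3 (Actions Questions; Outcomes): if the child had symptoms, whether the parent, for example, "went to a physician, filled a prescription for antibiotics, etc".
- Follow-ups 2 and 3 (Data Collection, item 3): health-care services in general, over-the-counter medicines, prescriptions filled.

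The terms differ in three ways: ED visits against physician visits or services in general; prescriptions received against filled; overall counts against actions taken when a child had symptoms. Antibiotic prescriptions appear at both times.

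The follow-up recall window is also loose. Both follow-ups refer to the course of the study, so one event could be reported twice. Study Design: RCT times these follow-ups from the end of the intervention, whereas Data Collection times them from baseline.

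**2. What the analysis does with the counts**

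The between-group tests take no covariates. The paired tests need the same measure at both times, which the overview does not show for actions. So no use of the counts is specified.

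**3. What adjustment could bring**

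Input: r, the correlation between prior and later use. The documents do not give it; 0.3 to 0.5 is assumed. In a linear model:

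- variance remaining = 1 − r²
- equivalent sample-size multiple = 1 / (1 − r²)
- reduction in standard error = 1 − √(1 − r²)

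Results:

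- r = 0.3: 1 − 0.09 = 0.91; 1 / 0.91 = 1.10; standard error about 5% smaller
- r = 0.4: 1 − 0.16 = 0.84; 1 / 0.84 = 1.19; about 8% smaller
- r = 0.5: 1 − 0.25 = 0.75; 1 / 0.75 = 1.33; about 13% smaller

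Over a wider assumed range, r = 0.2 leaves 0.96 of the variance and r = 0.7 leaves 0.51.

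These factors belong to linear models. In logistic regression, adjustment usually raises the standard error of the log odds ratio and changes the quantity estimated from a marginal to a conditional odds ratio. They do not transfer directly to logistic or negative binomial models.

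**4. How many parents inform the comparison**

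The plan needs 64 per group and recruits 90 to allow for dropout. Informative action data come from parents whose child had symptoms. If a share s of 64 completers qualifies (assumed), the number per arm is 64 × s: about 19 at s = 0.3, 32 at 0.5 and 45 at 0.7. A single topic would have fewer.

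**5. Why the actions must be separated by topic**

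Both arms receive blogshots. Under Study Design: RCT, Group A's topics are throat swabs, cough and cold remedies, and antibiotics in asthma exacerbations. Group B's are antibiotics for sore throat, bronchiolitis and otitis media. Each arm is the comparator for the other's topics. A pooled measure such as any antibiotic use mixes effects expected to favour A with effects expected to favour B, and they can cancel. Adjustment cannot repair that.

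**The case against.** The strongest reply is that the documents contain only an overview of the questionnaires. The follow-up items are introduced as examples and left open-ended, and seeking health-care services can include an ED visit. A look-back missing from an overview may be present in the instrument. This stands. A reader might infer that the trial cannot report ED use, but the text does not support that.

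A second reply is that a randomised comparison of actions needs no matching baseline item, that no change from baseline in actions is planned, and that chance imbalance is already reflected in the confidence interval. This also stands: the unadjusted comparison is unbiased in expectation. A reader might infer that the actions outcome has no usable baseline. That goes too far, because the counts can describe balance between arms and can serve as covariates even though the wording does not match.

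Third, the paired-test sentence is generic, so the counts are not shown to be excluded from every analysis. The accurate statement is that no use of them is specified.

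Fourth, actions are exploratory and fall outside the stated objective of awareness, knowledge and expectations. This limits the weight of the point. None of these replies gives a reason to leave a plausible predictor, already collected, out of the comparison.

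**Conclusion.** The point holds as a matter of efficiency and clarity in an exploratory domain. The trial collects prior ED and antibiotic use, specifies no role for it, and plans only unadjusted group tests. The actions comparison therefore forgoes available precision and leaves chance imbalance in prior use unadjusted. It is not biased by this, and the knowledge comparison is untouched.

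The gain is unknown. The linear-model range of 0.91 to 0.75 of the variance rests on an assumed r of 0.3 to 0.5 and is a rough guide only. The number of informative parents may be below 64 per arm. The differences in wording and the unstated look-back are matters to clarify; they do not show that any item is missing from the follow-up questionnaires.

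**What to change.** In the Plan for Data Analysis, state that arms will be compared on actions with a regression model adjusted for the baseline ED-visit and antibiotic-prescription counts: logistic for any use, negative binomial where counts are recorded. Report estimates with 95% confidence intervals and label the results exploratory.

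Define the actions by blogshot topic, so that topics where A is the intervention are not pooled with topics where B is. Sore throat carries a message in each arm (swab in A, antibiotics in B), so the definition must name the action as well as the condition. Keep over-the-counter medicine use, which bears on Group A's cough and cold topic. Reconcile the topic allocation first: the Knowledge Questions paragraph links bronchiolitis to A and asthma to B, the reverse of Study Design: RCT.

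Where the instruments can still be changed, use the same wording and a fixed recall window for ED visits and antibiotic prescriptions at baseline, follow-up 2 and follow-up 3. Otherwise, use the existing counts as they are.

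The analysis change takes a few sentences and no new data. Aligning the items makes the questionnaire slightly longer. Topic-specific analysis will give small numbers and wide intervals, which the report should acknowledge.
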